4 STUDY DESIGN

4.1 Overall design

4.1.1 Overview

This is a randomised, double-blind, placebo-controlled, parallel, global, dose-finding, Phase 2b study to assess the efficacy and safety of verinurad and allopurinol in patients with chronic kidney disease and hyperuricaemia. Patients who meet the eligibility criteria will be randomised in a 1:1:1:1:1 ratio to high, intermediate or low dose of verinurad plus allopurinol, allopurinol or placebo.

As of Protocol Version 5.0 and following a blinded interim analysis in September 2020, the study design was modified to include a new dosing regimen. All patients with Visit 9 (47 weeks) occurring after implementation of the amendment and IP is available (approximately 01 May 2021, ie, approximately half of planned patients randomized) will be treated with the new dosing regimen. Under the new dosing regimen all patients will continue with the same dose of verinurad and allopurinol as previously, except patients randomized to the low dose of verinurad (3 mg), which will be switched to treatment with 24 mg verinurad.

Also, following implementation of the amendment, all subjects will discontinue therapy after 60 weeks (Visit 10). Patients that have conducted Visit 10 before the implementation of the amendment will discontinue therapy at their next scheduled visit.

The new treatment regimen will be dispensed to patients for which Visit 9 falls on or after the last of the following dates:

- the date of availability at site of IP suitable for the new treatment regimen,
- the date of the Regulatory Authority approval of Protocol Version 5.0 in the respective country, and
- the date of the Ethics Committee/Independent Review Board approval of Protocol Version 5.0 in the respective country/site.

A patient in the new dosing regimen who is still on treatment, who has not been down-titrated and has signed Informed Consent Form (ICF) for the new dosing regimen, will receive the new treatment at Visit 9. Patients who do not consent should be discontinued from the study at a subsequent visit. If the patient has passed Visit 9 before the dates listed above, they will remain on the initial dosing regimen.

A total of 725 patients (145 per initial dosing regimen arm) at around 200 sites in around 15 countries will be randomised with equal probability to 1 of the initial dosing regimens 5 treatment arms.

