4.1.2.9 Week 47 (Visit 9)

At the time of implementation of Protocol Version 5.0, a new dosing regimen will be introduced to assess the higher dose of 24 mg verinurad. Patients in the 3 mg verinurad cohort

who will have Visit 9 planned after the amendment implementation in the respective country/site and who have signed ICF for the new dosing regimen will be switched to 24 mg dose at Visit 9. Patients who do not consent should be discontinued from the study at a subsequent visit.

To introduce the new 24 mg dose, a new dosing regimen will be initiated across treatment arms to maintain blinding. For verinurad dosing, all patients in the new dosing regimen will receive 2 capsules through addition of a matching placebo capsule, with the exception of those who switched from the 3 mg to 24 mg dose, where two 12-mg verinurad capsules will be given. Allopurinol dosing will remain the same.

Note: Patients will only be allowed to switch to the new dosing regimen's treatments introduced under Protocol Version 5.0 if the patient's eGFR was \geq 30 mL/min/1.73m² at Visit 8. Management of patients with eGFR <30 mL/min/1.73m² at Visit 9 should be discussed with the medical monitor.

- Place phone calls on the day before the visit to remind patients to record the time and date of the study medication intake on the day of the visit
- Collect first morning void samples from 3 days before visit
- Collect untaken study medication
- Update concomitant medication
- Record AEs
- Record vital signs
- Record weight
- Obtain blood samples for post-dose PK and sUA (drug taken at home, date and time of drug intake should be recorded)
- Obtain blood samples for efficacy assessments (s-UA, creatinine, eGFR, Cystatin C, NTproBNP)
- Perform pregnancy urine dipstick test for women of childbearing potential; after 2 positive urine tests, a serum pregnancy test is to be done by central laboratory
- Prior to Protocol Version 5.0, IVRS/IWRS and dispense titration Step-3 dose (Note: Titration to step-3 target dose will only be allowed if the patient's eGFR was ≥30 mL/min/1.73m² at Visits 3 and 4.)
- Dispense containers for morning voids

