4.2 Scientific rationale for study design

The purpose of the study is to establish the dose of verinurad combined with allopurinol 300 mg once daily that will elicit the desired response; ie, reduction in UACR at 6 months. UACR is a measurement of albuminuria, it was chosen because changes in UACR can be detected early in response to treatment, and these changes, if substantial, correlate with progression of CKD, deterioration in eGFR, and hard outcomes. Therefore, change in UACR is regarded as an appropriate endpoint. In this study, change in UACR at 6 months of treatment is the primary endpoint for the efficacy evaluation of treatment with the combination of verinurad and allopurinol vs. placebo. A key secondary objective is evaluation of verinurad plus allopurinol on the reduction in UACR at 12 months. Additional secondary endpoints include changes from baseline in sUA, eGFR, cystatin C, creatinine and NT-proBNP. Further, standard safety parameters such as AEs, SAEs, and laboratory evaluations will be employed to assess the safety profile of the study drugs. Verinurad, allopurinol and oxypurinol plasma concentrations over time will also be measured.

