5.3.2 Alcohol intake

Investigational product should not be taken within an hour of ingesting alcohol. There are no restrictions on combining IP intake with caffeine or nicotine intake, but it is recommended to take the IP with food.

5.3.3 **MRI** procedures:

Patients will be instructed to drink at least 250 mL water within 1 hour before the scan.

5.4 **Pre-screen and screen failures**

The study will include a two-step screening procedure:

- Pre-screening (Visit 1): Patients with sUA <6.0 mg/dL, eGFR <25 mL/min/1.73 m² or • UACR <30 mg/g will be classified as pre-screen failures. A single repeat test is permitted if initial sUA, eGFR or UACR results are not in the eligible range.
 - Patients are eligible to pre-screen up to 2 times. There are no time restrictions between the two pre-screening visits.
 - The visit at which the pre-screening criteria are met should be within Weeks -6 to -1.
 - Once patients have met the criteria set in pre-screening, patients are eligible for _ screening.
 - If a patient passes pre-screening but does not yet satisfy the inclusion/exclusion criteria, the subject may wait to screen at the discretion of the investigator.
- Screening (Visit 2): Patients who do not meet all eligibility criteria based on the full Visit 2 assessment will be classified as Screen Failures.

- A single repeat of an out-of-eligibility range assessment is permitted.
- Patients can undergo screening up to 2 times.
- The same IXRS ecode should be used for the re(pre)screened patient.

Screen failures are defined as patients who signed the ICF to participate in the clinical study but are not subsequently randomly assigned to study treatment. A minimal set of screen failure information is required to ensure transparent reporting of screen failure patients to meet the Consolidated Standards of Reporting Trials (CONSORT) publishing requirements and to respond to queries from regulatory authorities. Minimal information includes demography, screen failure details, eligibility criteria, and any SAE.

These patients should have the reason for study withdrawal recorded in the electronic case report form (eCRF).

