6.1 Treatments administered

6.1.1 Investigational products

	IP 1	IP 2
Study treatment name:	Verinurad or matching placebo	Allopurinol or matching placebo
Dosage formulation:	Capsule	Tablet
Route of administration	Oral	Oral
Dosing instructions:	3, 7.5, or 12 mg to be taken, one time a day	100, 200, or 300 mg to be taken, one time a day
Packaging and labelling	Verinurad capsules will be packaged in bottles. Each bottle will be labelled in accordance with Good Manufacturing Practice (GMP) Annex 13 and per country regulatory requirement	Allopurinol tablets will be packaged in bottles. Each bottle will be labelled in accordance with Good Manufacturing Practice (GMP) Annex 13 and per country regulatory requirement
Provider	AstraZeneca	AstraZeneca

Table 6Study treatments (prior to Protocol Version 5.0)

IP Investigational product

At the time of implementation of Protocol Version 5.0, a new dosing regimen will be introduced to assess the higher dose of 24 mg verinurad. Patients in the 3 mg verinurad cohort who will have Visit 9 after the amendment implementation in the prospective country/site and who have signed ICF for the new dosing regimen will be switched to 24 mg dose at Visit 9. Patients who do not consent should be discontinued from the study at a subsequent visit. To introduce the new 24 mg dose, a new dosing regimen across treatment arms will be initiated to maintain blinding in all study cohorts. All patients in the new dosing regimen will receive 2 capsules, as patients switched from 3 mg to 24 mg dose will receive two 12-mg verinurad capsules, and the bottles differentiated by colour, will be administered to all other patients. Patients on 24 mg verinurad need to take two 12-mg verinurad capsules. To match, patients in the other arms must take 2 capsules for blinding purposes. Patients will be instructed to take one capsule out of two different bottles every day. Allopurinol dosing will remain the same.

	IP 1	IP 2
Study treatment name:	Verinurad or matching placebo	Allopurinol or matching placebo
Dosage formulation:	Capsule	Tablet
Route of administration	Oral	Oral
Dosing instructions:	3*, 7.5, or 12 mg to be taken, one time a day from two differently coloured bottles Patients from 3 mg dose who will be switched to 24 mg will receive 24 mg as two 12-mg capsules**	100, 200, or 300 mg to be taken, one time a day

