Packaging and labelling	Verinurad capsules will be packaged in bottles. Each bottle will be labelled in accordance with Good Manufacturing Practice (GMP) Annex 13 and per country regulatory requirement	Allopurinol tablets will be packaged in bottles. Each bottle will be labelled in accordance with Good Manufacturing Practice (GMP) Annex 13 and per country regulatory requirement
Provider	AstraZeneca	AstraZeneca

Table 7Study treatments (after implementation of Protocol Version 5.0)

IP Investigational product

*3 mg verinurad capsules will only be used for down-titration for patients on the new dosing regimen as of Protocol Version 5.0.

**Patients on 24 mg verinurad need to take two 12-mg verinurad capsules. To match, patients in the other treatment arms must take 2 capsules to maintain the blind. Patients will be given two different bottles with differently coloured labels. Patients will be instructed to take one capsule from each of two different bottles every day. Patients who do not tolerate the new dosing regimen will be down-titrated to the initial dosing regimen (ie, patients on 24 mg will be down-titrated to 3 mg, and patients in other cohorts will not be dispensed the matching placebo capsule).

The verinural capsules release verinural over 8 h, hence the formulation is referred to as ER8 (Extended Release over 8 h).

Study treatments will be titrated in discrete steps as shown in Table 8. Titration steps will be spaced at 4-week (± 1 week) intervals to minimise the risk of skin reactions to allopurinol. Patients unable to tolerate the stepped dosage may be down-titrated only by reversing the assigned steps within treatment group, and verinurad and allopurinol dosages cannot be unpaired from the titration schedule. Patients who cannot tolerate the step-1 dose will be discontinued from IP and be followed for the remainder of the study.

At Visit 5 (approximately 8 weeks after randomisation) through Visit 9, titration to step-3 target dose will only be allowed if the patient's eGFR was \geq 30 mL/min/1.73m² at Visits 3 and 4.

When the new dosing regimen is introduced under Protocol Version 5.0, patients who were down-titrated due to intolerance in the initial dosing regimen will not switch treatment to the new dosing regimen. These patients will instead remain on the same treatment after Visit 9.

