Patients who do not tolerate the new dosing regimen will be down-titrated to the initial dosing regimen (ie, patients on 24 mg will be down-titrated to 3 mg, and patients in other cohorts will not be dispensed the matching placebo capsule).

Patients will only be allowed to switch to the new dosing regimen introduced under Protocol Version 5.0 if the patient's eGFR was \geq 30 mL/min/1.73m² at Visit 8. Management of patients with eGFR <30 mL/min/1.73m² at Visit 9 should be discussed with the medical monitor.

In case patient down-titration was done in error, the patient can be up-titrated only after consultation with the medical monitor.

	Step 1 - titration	Step 2 - titration	Step 3 - target dose
	(verinurad/allopurinol)	(verinurad/allopurinol)	(verinurad/allopurinol)
High Dose (mg)	3/100	7.5/200	12/300
Intermediate Dose (mg)	3/100	7.5/200	7.5/300
Low Dose (mg)	3/100	3/200	3/300
Allopurinol alone (mg)	0/100	0/200	0/300
Placebo (mg)	0/0	0/0	0/0

Table 8Titration schedule

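### The Visit 9 switch to 24 mg verinurad does not require titration step 3, so a low-dose patient held at 3/200 for early low eGFR would receive 24 mg with allopurinol left at 200 mg

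*Supplement*

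**What the plan says.** Two eGFR rules in the protocol bear on the dose at Visit 9.

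- **Step 3.** Section 6.1.1: "At Visit 5 (approximately 8 weeks after randomisation) through Visit 9, titration to step-3 target dose will only be allowed if" eGFR was at least 30 mL/min/1.73 m² at Visits 3 and 4. The visit descriptions in Section 4.1.2 and the footnotes to the schedule of activities repeat this.
- **Switch to 24 mg.** Section 6.1.1: "Patients will only be allowed to switch to the new dosing regimen introduced under Protocol Version 5.0 if the patient's eGFR was". The required value is 30 or more, measured at Visit 8. Section 4.1.2.9 says the same. Section 4.1.1 adds who gets the new treatment at Visit 9: a patient "who is still on treatment, who has not been down-titrated and has signed Informed Consent Form (ICF) for the new dosing regimen, will receive" it. Section 6.6 bars patients who were down-titrated and are below their randomised verinurad dose.

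At the switch the 3 mg cohort takes two 12 mg verinurad capsules, and "Allopurinol dosing will remain the same" (Section 6.1.1).

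Section 4.2 gives the aim: "The purpose of the study is to establish the dose of verinurad combined with allopurinol 300 mg once daily". Section 4.3 explains that verinurad is titrated together with allopurinol, up to 300 mg, to avoid oversaturating the urine with urate.

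**The concern.** The step-3 rule looks at eGFR at Visits 3 and 4, and the switch rule looks at eGFR at Visit 8. Nothing links them. A patient can fail the first, stay on 200 mg allopurinol, and pass the second.

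In the low-dose arm the verinurad dose is 3 mg at every step, so a hold at step 2 shows only in the allopurinol dose. The switch rules never look at that dose. The result is the trial's highest verinurad dose on less allopurinol than the protocol intends, in patients whose early eGFR was among the lowest enrolled. Section 4.3 itself notes that low renal function raises verinurad exposure.

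The patient data cited for verinurad with allopurinol (Sections 2.2.1 and 4.3) used 300 mg allopurinol, with verinurad up to the equivalent of 12 mg of the ER8 capsule. At stake is dosing consistency and safety for a small group. The primary result is not affected.

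**Working it through.** **Tracing one low-dose patient through the rules** (eGFR 28 at Visit 3, 31 at Visit 8, consenting, still on treatment):

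| Step | Rule | Outcome |
|---|---|---|
| Entry | Section 5.4 makes "Patients with sUA <6.0 mg/dL, eGFR <25 mL/min/1.73" m² a pre-screen failure, so 25 and above may enter | Eligible on eGFR |
| Visit 4 | Section 4.1.2.4 dispenses step 2 with no eGFR condition | 3/200 |
| Visits 5 to 9 | Step 3 needs eGFR of at least 30 at Visits 3 and 4 | Held at 3/200; later recovery does not reopen step 3 |
| Visit 9: on treatment, consented | Section 4.1.1 | Met |
| Visit 9: not down-titrated | Sections 4.1.1, 6.1.1 | Met: never up-titrated to step 3, never reduced |
| Visit 9: not below randomised verinurad dose | Section 6.6 | Met: 3 mg equals 3 mg |
| Visit 8 eGFR at least 30 | Sections 4.1.2.9, 6.1.1 | Met: 31 |
| Result | 24 mg verinurad, allopurinol unchanged | **24/200** |

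In the high-dose arm the same eGFR history holds the patient at 7.5/200 (Table 8).

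**Can both rules reach the same patient?** Visit 9 (Week 47) minus Visit 5 (Week 8) is 39 weeks, or 273 days. Section 4.1.1 expects the new regimen from about 01 May 2021, and 273 days earlier is 01 August 2020. The version history dates the step-3 eGFR limit to Version 4, 06 August 2020, five days later. Nearly all patients switching from May 2021 would therefore have Visit 5 on or after that date, although local implementation may lag.

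**Size of the dose discrepancy.**

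- Intended pair: 24/300 = 0.08.
- Pair under the gap: 24/200 = 0.12.
- Ratio: 0.12/0.08 = 1.5.
- Low-dose against high-dose arm for the same early eGFR history, both on 200 mg allopurinol: 24/7.5 = 3.2. The intended contrast at step 3 is 24/12 = 2.0, so the part beyond it is 3.2/2.0 = 1.6.

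**Number affected.** The documents give no count. Assumptions:

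- About half of the 145 low-dose patients reach Visit 9 under Version 5.0, ignoring dropout: 145/2 = 72.5.
- 2% to 15% of them were held for eGFR below 30 at Visit 3 or 4.
- 20% to 50% of those held have eGFR of 30 or more at Visit 8.

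Low end: 72.5 × 0.02 × 0.20 = 0.29. High end: 72.5 × 0.15 × 0.50 = 5.44.

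**The case against.** Several texts could be read as closing the gap.

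- **Visit 9 dispensing row.** Table 1 marks only step-3 dispensing at Visit 9, with the footnote requiring eGFR of at least 30 at Visits 3 and 4. A patient barred from step 3 would hardly be meant to go above it. But Section 4.1.2.9 ties that dispensing note to the period before Version 5.0, the footnote limits step 3 only, and the footnote on the switch omits any step.
- **Target dose.** The synopsis says treatment continues at target dose after Visit 9. That describes duration and is not a condition for switching.
- **Pairing clause.** Section 6.1.1 says "verinurad and allopurinol dosages cannot be unpaired from the titration schedule". The clause sits in a sentence about patients who cannot tolerate a dose, and Table 8 has no 24 mg row to supply a partner dose. Read as a general rule, it would itself conflict with 24/200.
- **Medical monitor.** The referral covers eGFR below 30 at Visit 9, so it misses a patient who has recovered.
- **IVRS/IWRS.** Its user manual is not among the documents and may block the switch. This stands: the finding is limited to the protocol text.

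Other points carry weight on size. The amendment deliberately doubles the ratio, from 12/300 = 0.04 to 24/300 = 0.08, and the documents do not use this ratio as a safety measure. The percentages behind the patient count have no source in the protocol, and the high end is generous because dropout, non-consent and down-titration are ignored. Section 4.3 reports a verinurad peak concentration below half of that expected, and Appendix F gives renal monitoring and stopping rules. These temper the likely consequence but do not supply the missing condition.

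**Conclusion.** The concern holds as a reading of the Version 5.0 text. A low-dose patient held at step 2 for early eGFR below 30, never down-titrated, and at 30 or more at Visit 8 qualifies for 24 mg verinurad on 200 mg allopurinol. The discrepancy due to the gap is a factor of 1.5 in the verinurad-to-allopurinol ratio, for up to about 13 weeks. The 3.2-fold difference between arms describes what the rules produce. It includes the intended rise to 24 mg and is not a harm estimate.

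The group is small on the assumptions above, possibly less than one patient. The documents quantify no effect on urinary urate or renal adverse events, and none is claimed. Nor is any bias in the 12-month comparison. Severity is minor. Confidence in the reading of the rules is high; what the IVRS/IWRS would actually do is unknown.

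**What to change.** In every section that states the switch conditions (1.2, 4.1.1, 4.1.2.9, 6.1.1 and 6.6), allow the switch only if the patient:

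- is at titration step 3 (300 mg allopurinol or matching placebo) at Visit 9,
- has not been down-titrated, and
- had eGFR of at least 30 mL/min/1.73 m² at Visit 8.

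The existing on-treatment and consent conditions stay. Patients below step 3 should remain on their current treatment to Week 60, as Section 6.1.1 already provides for patients down-titrated for intolerance. Program the check identically for all five arms in the IVRS/IWRS, so that it reveals nothing about allocation. Aligning the down-titration wording of Section 6.6 with Section 4.1.1 at the same time is editorial.

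The cost is protocol wording, one system check at Visit 9, and slightly smaller 24 mg and double-dose comparison groups.

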1 PROTOCOL SUMMARY

1.1 Schedule of activities (SoA)

Visit	1 (Pre- Screening)	2 (Screening)	3 (Randomis ation)	4	5	6	7	8 (Primary Analysis)	9 ^a	10 ^a See EOT visit in Table 2	Details in CSP section or Appendix
Week	-6 to -1	-4 to 0	0	4	8	12	20	34	47	60	
Window			NA	±7d	±7d	±7d	±7d	±7 d	±7d	±7d	
Informed consent for blood draw and urine collection	х										Appendix A3 page 95
Spot UACR	х										Sections 5.1.1 and 4.1.2.1
Blood test for creatinine, sUA, and eGFR	х										Sections 5.1.1 and 4.1.2.1
Full signed informed consent		х									Appendix A3 page 95
Inclusion /exclusion criteria		х	х								Sections 5.1 and 5.2
Dispense urine containers for FMV urine collection	х	х	x	х	x	x	х	x	х	Xp	Section 8.1.1
Routine clinical procedures			·								
Demography		Х									Section 5.1
Full physical examination		Х								Х	Section 8.2.2
Brief physical examination			Х	Х	Х	x		X			Section 8.2.2
Medical history and comorbid conditions		x									Sections 5.1 and 5.2
Vital signs ^c		Х	Х	Х	Х	X	Х	X	Х	Х	Section 8.2.3
Height		Х									Section 8.2.2
Weight		Х	Х	Х	Х	X	Х	X	Х	Х	Section 8.2.2

 Table 1
 Schedule of activities (SoA), screening and treatment period

Visit	1 (Pre- Screening)	2 (Screening)	3 (Randomis ation)	4	5	6	7	8 (Primary Analysis)	9 ^a	10 ^a See EOT visit in Table 2	Details in CSP section or Appendix
Week	-6 to -1	-4 to 0	0	4	8	12	20	34	47	60	
Window			NA	±7d	±7d	±7d	±7d	±7d	±7d	±7d	
ECG		х	Х			X		X		х	Section 8.2.4
Concomitant medication		х	Х	х	X	X	Х	X	Х	х	Section 6.5
Routine safety measurements											
Adverse events ^d		Х	Х	Х	X	X	Х	X	Х	Х	Section 8.3
Pregnancy test (serum or urine) ^e		х	x			x	х	x	x	Xb	Section 5.1
Sample for HLA genotyping ^f		Х									Sections 8.7.1 and 5.2
Safety laboratory assessments (including clinical chemistry, haematology, urinalysis)		х	x	х	x	x		x		x	Section 8.2.1
Biomarker analysis											
CCI											
Pharmacokinetic measureme	nts ^h	•									
Phone call to PK participants						X	X	X	Х	Х	
Pre-dose blood sample in all patients						x					Section 8.5
Pre- and post-dose PK/sUA blood samples in sub-group						x					Section 8.5

Table 1 Schedule of activities (SoA), screening and treatment period

Visit	1 (Pre- Screening)	2 (Screening)	3 (Randomis ation)	4	5	6	7	8 (Primary Analysis)	9ª	10 ^a See EOT visit in Table 2	Details in CSP section or Appendix
Week	-6 to -1	-4 to 0	0	4	8	12	20	34	47	60	
Window			NA	±7d	±7 d	±7d	±7 d	±7d	±7 d	±7d	
Post-dose blood sample in all patients							х	x	х	х	Section 8.5

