4.1.2.4 Week 4 (Visit 4)

- Collect first morning void samples from 3 days before visit
- Collect untaken study medication
- Update concomitant medication
- Record AEs
- Perform brief PE
- Record vital signs
- Record weight
- Obtain blood samples for clinical chemistry and haematology, and efficacy assessments (s-UA, creatinine, eGFR, Cystatin C, NT-proBNP)
- Obtain urine samples for safety assessment (dipstick urinalysis)
- IVRS/IWRS transaction and dispense titration Step-2 dose
- Dispense containers for morning voids

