4.1.2.8 Week 34 (Visit 8)

- Place phone calls on the day before the visit to remind patients to record the time and date
 of the study medication intake on the day of the visit
- Collect first morning void samples from 3 days before visit (for primary CCI biomarkers)
- Collect untaken study medication
- Update concomitant medication
- Record AEs
- Perform brief PE
- Record vital signs
- Record weight
- Obtain ECG
- - Obtain blood samples for clinical chemistry and haematology, efficacy assessments (s-UA, creatinine, eGFR, Cystatin C, NT-proBNP)
- Obtain blood samples for post-dose PK and sUA (drug taken at home, date and time of drug intake should be recorded)
- Obtain urine samples for safety assessment (dipstick urinalysis
- Obtain results/confirm availability of MRI renal and PWV evaluation for some patients
- Reactive hyperaemia evaluation for some patients
- Perform pregnancy urine dipstick test for women of childbearing potential; after 2 positive urine tests, a serum pregnancy test is to be done by central laboratory
- IVRS/IWRS and dispense titration Step-3 dose (Note: Titration to step-3 target dose will
 only be allowed if the patient's eGFR was ≥30 mL/min/1.73m² at Visits 3 and 4.)
- Dispense containers for morning voids

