6.6 Dose modification

Study treatments will be titrated in discrete steps as shown in Table 8. Titration steps will be spaced at 4-week intervals to minimise the risk of skin reactions to allopurinol. Patients unable to tolerate the stepped dosage may be down-titrated only by reversing the assigned steps within treatment group, and verinurad and allopurinol dosages cannot be unpaired from the titration schedule. Patients who cannot tolerate the step-1 dose will be discontinued from IP and be followed for the remainder of the study.

When the new dosing regimen is introduced under Protocol Version 5.0, patients unable to tolerate the new dosing regimen will be down-titrated to the initial dosing regimen (ie, patients on 24 mg will be down-titrated to 3 mg, and patients in other cohorts will not be dispensed the matching placebo capsule). Additionally, patients who have been down-titrated and are receiving less than the randomized dose of verinurad/matching placebo at Visit 9 will not switch to the new dosing regimen introduced under Protocol Version 5.0.

In case patient down-titration was done in error, the patient can be up-titrated only after consultation with the medical monitor.

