8.4.5 Management of IP-related toxicities

Study drug should be discontinued immediately at the first sign of a skin rash or other signs which may indicate an allergic reaction, and patients should be maintained in the study for safety surveillance. In cases of intolerance (gastrointestinal, headache, or other mild AEs) from the combination IP, dosage will be down-titrated as described in Section 6.1.

Patients developing renal-related or kidney stone AEs, or creatinine elevations during treatment should be managed in accordance with Appendix F.

Patients developing elevated liver transaminase tests should be managed in accordance with Appendix E.

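### The switch from 3 mg to 24 mg verinurad at Week 47 has no ALT, AST or bilirubin measurement at the dispensing visit

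*Supplement*

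**What the plan says.** **Conditions for the switch.** Section 6.1.1 of the protocol says "Patients will only be allowed to switch to the new dosing regimen introduced under Protocol Version 5.0" if eGFR was at least 30 mL/min/1.73 m² at Visit 8; Section 4.1.2.9 repeats this. Under Section 4.1.1, a patient who is still on treatment, has not been down-titrated and "has signed Informed Consent Form (ICF) for the new dosing regimen, will receive the new treatment at Visit 9". Section 6.6 adds that down-titrated patients "receiving less than the randomized dose of verinurad/matching placebo at Visit 9 will not switch to the new dosing regimen". None of these conditions is a liver test.

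**Blood taken at Visit 9.** In Table 1 the row "Safety laboratory assessments (including clinical chemistry, haematology, urinalysis" is blank at Visit 9. Apart from PK and sUA samples, Section 4.1.2.9 lists only: "Obtain blood samples for efficacy assessments (s-UA, creatinine, eGFR, Cystatin C, NTproBNP". ALT, AST and bilirubin belong to the safety panel (Table 14), not to the efficacy panel (Table 11).

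**Blood taken at neighbouring visits.** Visit 8 (Week 34) has the panel: "Obtain blood samples for clinical chemistry and haematology, efficacy assessments". So does the end-of-treatment visit at Week 60 (Section 4.1.2.12). The titration steps at Weeks 4 and 8 are dispensed at visits with the panel; for Week 4 the text is "Obtain blood samples for clinical chemistry and haematology, and efficacy assessments".

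**Handling of liver results.** Section 8.4.5 says: "Patients developing elevated liver transaminase tests should be managed in accordance with Appendix E". Appendix E 3 provides an immediate central-laboratory alert for an isolated ALT or AST of at least 3xULN, or total bilirubin of at least 2xULN, followed by prompt review of all earlier results. Section 8.2.1 allows extra safety samples at the investigator's discretion.

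**The concern.** Visit 9 is where 3 mg patients receive their first verinurad increase. In their arm the Week 4 and Week 8 steps raise only allopurinol (Table 8), so 3 mg to 24 mg is a single step. At this visit the plan measures creatinine and eGFR but no liver enzyme.

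Two things are lost:

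- **Baseline.** No switcher has a scheduled liver value from the day 24 mg starts. If ALT is raised at Week 60, that patient's record cannot show whether the rise began on 3 mg after Week 34 or on 24 mg.
- **Detection.** A rise that begins between Weeks 34 and 47 is not picked up by any scheduled test before the dose goes up. The discontinuation criterion in Section 7.1 (ALT or AST at least 3xULN together with bilirubin at least 2xULN) and the alerts in Appendix E 3 have no scheduled data to act on at that point.

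Sections 2.3 and 4.3 describe earlier use of 24 mg of this formulation for 7 days in healthy subjects. Here patients with CKD take it for about 13 weeks, so individual safety data on this dose are worth having.

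**Working it through.** **Plan's own figure.** Section 2.3 limits 24 mg exposure to approximately 13 weeks. From Table 1: 60 − 47 = 13 weeks, which agrees.

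**Which visits have the liver panel.** The safety-laboratory row of Table 1 is marked at Visits 2, 3, 4, 5, 6, 8 and 10 and blank at Visits 7 and 9. Section 4.1.2.9 agrees for Visit 9.

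**Distance of required liver results from each change of dose:**

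| Change | Panel at the visit | Previous panel | Next panel |
|---|---|---|---|
| Week 4, step 2 | yes | Week 0, 4 weeks before | Week 8, 4 weeks after |
| Week 8, step 3 | yes | Week 4, 4 weeks before | Week 12, 4 weeks after |
| Week 47, switch to 24 mg | no | Week 34, 47 − 34 = 13 weeks before | Week 60, 60 − 47 = 13 weeks after |

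Each visit has a ±7-day window, so a gap between two visits can vary by ±2 weeks. Each 13-week gap runs from 11 to 15 weeks. The full stretch between required results is 60 − 34 = 26 weeks (24 to 28). The Week 12 to Week 34 stretch is also long, 34 − 12 = 22 weeks, but holds no scheduled dose increase.

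**Size of the step.** 24/3 = 8 times the patient's own dose; 24/12 = 2 times the highest dose in the initial regimen.

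**Number affected.** Section 4.1.1 expects approximately half of the planned patients to come under the new regimen.

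- Switchers: 145/2 = 72.5, so at most about 72, before dropout, down-titration, refusal of consent and eGFR below 30.
- All arms: 725/2 = 362.5, so at most about 362.

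The documents give no rate of raised liver results at Week 34 or later, so no count of missed elevations is attempted.

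**After the fix.** With a Visit 9 liver test, the time from last liver result to switch falls from 13 weeks to 0, and the longest stretch without a required result around the switch falls from 26 to 13 weeks. The time from switch to first required result on 24 mg stays at 13 weeks. A further panel 4 weeks after the switch, at about Week 51 (47 + 4), would cut it to 4.

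**The case against.** The case for leaving the schedule alone has weight.

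- **No liver hazard is documented.** Section 2.3 names creatinine elevation as the main verinurad toxicity, and Section 8.3.9 lists cardiovascular events and creatinine changes as being of special interest. The eGFR condition and the Visit 9 creatinine address the named risk. This stands. A reader might infer that verinurad is a liver risk or that the switch is unsafe; the documents do not support that.
- **Week 34 elevations are already flagged.** The Appendix E 3 alert and review come 13 weeks before the switch, and Section 8 sends immediate safety concerns to the sponsor. This stands, and limits the point to rises that begin after Week 34 and to the missing baseline.
- **Prior exposure may be wider than 7 days.** A reader might infer that the 7-day study was the only use of 24 mg. The protocol does not say so. It also cites the wider programme and the blinded interim safety data, and it reports the highest verinurad exposures after 40 mg immediate-release. For the 24 mg dose here it expects Cmax below that of the 7-day study and AUC only slightly above.
- **Group comparison remains possible.** A concurrent double-dose placebo group exists (Section 9.4.2.2), so an excess of raised results on 24 mg could be seen between groups. This stands. What is lost is attribution in the individual patient.
- **The titration comparison is imperfect.** The 4-week spacing protects against allopurinol skin reactions, and allopurinol does not change at Week 47. That is a fair caution. The comparison shows only that the protocol elsewhere draws chemistry when it dispenses a new step.

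None of these safeguards requires a liver result at Visit 9.

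**Conclusion.** The point holds as a cheap improvement to safety monitoring. The largest verinurad step in the trial is dispensed at a visit without ALT, AST or bilirubin, and the last required result is 13 weeks old (11 to 15). At most about 72 patients therefore start 24 mg without a scheduled individual liver baseline, and a rise that begins between Weeks 34 and 47 has no scheduled detection before the switch.

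Confidence in the schedule facts is high: they follow from Table 1 and Section 4.1.2.9. The patient count rests on the protocol's estimate that about half of patients come under the new regimen. The clinical consequence is probably small, since no liver signal is reported and Week 34 elevations are reviewed.

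A reader might also infer that the switch contradicts exclusion criterion 11, or that it needs a liver gate at those limits. Criterion 11 applies at entry. Its bilirubin limit (1.5xULN) is stricter than the on-study trigger (2xULN), so using it as a gate would be a debatable choice. Such a gate, and a change to Appendix E 3 for the whole trial, are optional and not part of this conclusion.

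**What to change.** In all arms, so that the blind is kept, add ALT, AST and total bilirubin (or the full safety chemistry panel) to the blood draw already taken at Visit 9. Mark the safety-laboratory row of Table 1 at Visit 9 and add the matching line to Section 4.1.2.9.

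The chemistry is run centrally and study drug is dispensed at the end of the visit, so the result would be expected after dispensing. It serves as a baseline before 24 mg and as an early alert under the existing Appendix E 3 process, not as a condition for the switch.

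The cost is one extra assay for at most about 362 patients, with no added visit. If the sponsor also wants an earlier liver result on 24 mg, a panel about 4 weeks after the switch would provide it, but that needs an extra visit in all arms.
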